#### **Sample Size**

Sample size calculations were performed based on the precision of the moderate error rate as based on the surveillance error grid calculations. Given the goal to estimate the error rate to within 5% based on 95% confidence intervals, assuming 10 samples per patient and a moderate intraclass correlation coefficient (ICC) of 0.3, if the observed error rate is 5%, then 28 subjects (at least 271 paired samples) will be required to achieve this level of precision. Note that if you wish to estimate these levels with this precision for subgroups of your population, each subgroup will need to have this many subjects. Table 1 shows the number of samples required for different levels of precision and error rates under similar assumptions. Sample size calculations were performed using the online calculator by Dhand, N. K., & Khatkar, M. S. (2014).

**Table 1.** Samples required to achieve precision as described assuming 95% confidence, an ICC of 0.3, and 10 paired samples per subject. Number is subjects would be the number below divided by 10.

Error Rate	Absolute precision							
	0.03	0.04	0.05	0.06	0.07	0.08	0.09	0.10
20%	2527	1422	910	632	465	356	281	228
15%	2014	1133	725	504	370	284	224	182
10%	1422	800	512	356	262	200	158	128
5%	751	422	271	188	138	106	84	68

Primary outcome:

To address accuracy, glucose readings obtained from the CGMS will be compared with

- 1) blood glucose from the arterial blood gas (ABG) or peripheral/central venous catheter if arterial catheter not in use (standard of care in CVICU) while patients are in the CVICU
- 2) fingerstick point of care (POC) glucose when patients are on the regular floors

Other outcomes:

The following can be derived based on the average length of stay (LOS) of the study patients in the CVICU and the regular floors (current average of 24-36 hours, and a total hospital LOS of 4-5 days)

Cost savings: cost of CGMS device including sensor, transmitter versus cost of doing an ABG to obtain glucose levels (CVICU stay), and versus the cost of Accu-check Inform II meter, test strips, and lancets

Time savings: time it takes to perform and time it takes to have results based on an ABG or fingerstick POC on Accu-check Inform II

Blood waste: blood sample amount for an ABG or fingerstick POC on Accu-check Inform II

Variables:

Age

Gender

Race

Weight

Height

BMI

Systolic blood pressures

Diastolic blood pressures

Temperatures

Diabetes status (no known diagnosis, known diagnosis)

Type of diabetes

Type of cardiothoracic surgery

Presence of peripheral vascular disease

Presence of peripheral edema  
Presence of medications/substances that might interfere with the CGMS  
Glucose readings (lab, point of care, CGMS)  
Serum creatinine  
Intravenous insulin infusion rate  
Subcutaneous insulin doses  
Use of pressors/vasoconstrictors/vasodilators  
Intravenous fluids  
Medications administered in the hospital

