**Objectives**

To assess the accuracy of the continuous glucose monitor Dexcom G6 (or similar device) on patients with hyperglycemia, with or without known diagnosis of diabetes, after cardiovascular surgery.

To calculate potential cost savings, time savings, and blood waste compared to current care (point of care glucose through blood gas)

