#### Procedure:

Dexcom G6 has a sensor (see photo below) that goes underneath the skin to sense interstitial glucose.

It is attached to a transmitter.

The third component is a receiver. The receiver has to be within 10-15 feet from the patient. We will place this in a well-marked pouch/bag.

In the photo below, the purple is the sensor and the gray oval on top of it is the transmitter. The sensor is inserted first, then the transmitter is attached to it.

The sensor/transmitter will be applied pre-operatively in the preop holding area or in the operating room (before anesthesia induction) to the upper outer arm by a physician, nurse, nurse practitioner or physician's assistant. The insertion area can be cleaned with alcohol or betadine.

The glucose readings on the device will not be visible to the ICU/regular floor staff nor the patients.

At the end of 10 days or upon discharge from the hospital, which ever comes first, the sensor/transmitter will be removed.

Time-stamped data from the CGMS software will be compared with the correlated ABG or venous of Accu-check Inform II glucose reading

The data transmission occurs via Blue-Tooth from sensor to the receiver.

The data have do be downloaded within 2 weeks.

The sensor has an adhesive so that it can stick to the skin. Skin Tac can be used to increase the adhesion to the skin. An adhesive overpatch specifically coming from/approved by Dexcom can be used over the sensor as needed to increase adhesion. NOTE: OpSite or Tegaderm CANNOT be used over the sensor as this will decrease reliability.

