#### **Safety:**

The CGMS will be inserted on the outer arm after the site is cleaned. The insertion site will be inspected daily for signs of infection, or of allergy from the sensor, adhesive, or overpatch.

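### Time and blood savings are defined as gross upper bounds: no CGMS-side staff time is subtracted, and no share of tests replaced is stated

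*Combined protocol and SAP*

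**What the plan says.** The second objective is comparative: "To calculate potential cost savings, time savings, and blood waste compared to current care (point of care glucose through blood gas" (Objectives). The three outcomes that serve it are defined in the Sample Size section, under Other outcomes, where they are to be derived from the average length of stay.

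- For time: "Time savings: time it takes to perform and time it takes to have results based on an ABG or fingerstick POC on Accu-check Inform II".
- For blood: "Blood waste: blood sample amount for an ABG or fingerstick POC on Accu-check Inform II".
- For cost: "Cost savings: cost of CGMS device including sensor, transmitter versus cost of doing an ABG to obtain glucose levels" in the CVICU, and "versus the cost of Accu-check Inform II meter, test strips, and lancets" for the floors.

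The protocol describes work on the CGMS side. The sensor and transmitter are applied "to the upper outer arm by a physician, nurse, nurse practitioner or physician's assistant" (Procedure) and later removed. Under Safety, "The insertion site will be inspected daily for signs of infection, or of allergy from the sensor, adhesive, or overpatch". Procedure also names a receiver as the third component, and Sanitation provides receiver shields that are changed between patients.

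CGMS readings are hidden from staff and patients (Procedure), and testing by current methods continues throughout (Study Design). The variable list has no field for why an ABG was drawn or for staff minutes, and Statistical Methods gives no analysis for the second objective.

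**The concern.** A saving compared with current care is a difference: the burden of the tests no longer done, minus the burden of what replaces them. The time outcome contains only the first term. The time and blood outcomes also do not say how many tests would no longer be done. Length of stay combined with test frequency counts every test, so without a stated share the calculation defaults to all of them.

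The study data cannot correct this. Because the CGMS is masked, no test is withheld and replacement is never observed. Nor can an ABG drawn only for glucose be told apart from one that would have been drawn for blood gases anyway.

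At stake is how the second objective is read. A gross figure reported as a saving would favour the device in a resource argument that the study has not tested.

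**Working it through.** **The plan's own figure.** The plan states no savings figure, so there is none to reproduce. Its one computed design figure, 271 paired samples in 28 subjects, does reproduce, but it concerns the error rate and plays no part here.

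**Which outcomes are one-sided**

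| Outcome | Current-care side | CGMS side | Share of tests replaced |
|---|---|---|---|
| Time | ABG or fingerstick time | none named | not stated |
| Blood | ABG or fingerstick volume | none named; the sensor reads interstitial glucose, so there is nothing evident to subtract | not stated |
| Cost | ABG; meter, strips, lancets | sensor, transmitter | not stated |

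**What the documents allow one to compute.** The inputs are a stay of 24 to 36 hours, read as the CVICU stay (Sample Size, Other outcomes), and a test every 1 to 3 hours (Study Design).

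- Fewest tests: 24 / 3 = 8.
- Most tests: 36 / 1 = 36.

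The gross count is therefore 8 to 36 CVICU tests per stay. Some may be venous rather than arterial samples.

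**From gross to net.** Let f be the share of tests replaced and g the CGMS-side burden as a fraction of the current-care burden. Then

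net = (f − g) × gross, and gross / net = 1 / (f − g).

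Gross equals net at f = 1 and g = 0; for any lower f or higher g, gross exceeds net. The documents give neither f nor g, so the values below are assumptions for illustration.

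| f | CVICU tests avoided | gross/net, g = 0 | gross/net, g = 0.1 |
|---|---|---|---|
| 1.00 | 8–36 | 1.00 | 1 / 0.90 = 1.11 |
| 0.75 | 6–27 | 1 / 0.75 = 1.33 | 1 / 0.65 = 1.54 |
| 0.50 | 4–18 | 1 / 0.50 = 2.0 | 1 / 0.40 = 2.5 |
| 0.25 | 2–9 | 1 / 0.25 = 4.0 | 1 / 0.15 = 6.7 |

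For blood, g = 0 is the natural reading, and only f matters. For staff time, both matter. When the reason for f below 1 is that some ABGs are drawn anyway, the ratios apply to the ABG component and not to floor fingersticks.

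**Staff time, on assumed inputs.** Assume 12 floor tests, 2 to 5 staff minutes per test, 20 to 40 minutes of CGMS handling per stay, and every test replaced.

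- Tests per stay: 8 + 12 = 20 to 36 + 12 = 48.
- Gross time: 20 × 2 = 40 min to 48 × 5 = 240 min.
- Share removed by CGMS handling: from 20 / 240 = 8% to 40 / 40 = 100%.

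The upper extreme pairs the fewest and shortest tests with the longest handling. The width of the range shows that the assumptions, not the documents, set the size.

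**The case against.** The strongest reply is that the objective promises only potential savings, and that in a masked accuracy study this means what could be saved, not a measured net effect. That reading is fair. It supports labelling the figure an upper bound, but it does not justify leaving CGMS time out of a comparison with current care.

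Several narrower objections stand:

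- A reader might infer that all three outcomes are one-sided. Cost is not: the device is set against ABG and fingerstick costs. The direction of any bias in cost is undetermined. Omitting the receiver would overstate savings. Charging a full transmitter per patient, when Sanitation allows cleaning and reuse if supply runs short, would understate them. The receiver is itself shared between patients, and the named components need not be an exhaustive list.
- A reader might infer that the plan assumes every test is replaced. No section says so. The cost wording refers to an ABG done to obtain glucose, which can be read as excluding ABGs drawn for other reasons. The blood and time definitions carry no such qualifier, however, and no listed variable would identify the ABGs meant.
- For blood, one-sidedness adds no bias of its own; only the replacement share does.
- The time definition joins two quantities, time to perform and time to result. CGMS handling reduces the saving in the first. On the second, the device reads every 5 minutes (Data), so the two should not be netted together.
- Some CGMS work, such as the daily inspection or the receiver pouch, may exist only because this is a study. Timing all of it would overstate the routine burden.

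**Conclusion.** The point holds for time and blood. As defined, time savings leaves out CGMS-side staff time, and neither time nor blood states a replacement share, so a derivation from length of stay gives gross upper bounds. For staff time, any routine CGMS handling puts the gross figure above the net saving. For blood, the gross figure exceeds the saving only if some tests would still be done.

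The stronger conclusion, that savings will be overstated by a known factor, is not supported. Only the 8 to 36 CVICU tests per stay follow from the documents, and that rests on reading the 24 to 36 hours as the CVICU stay. The ratios of 1.33, 2 and 4 are illustrations for an assumed 25%, 50% and 75% of ABGs drawn anyway, and the staff-time range is assumed in every other input. No direction of bias can be claimed for cost.

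These are descriptive secondary outcomes. The change is worth making, but the primary accuracy analysis and the sample size do not depend on it.

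**What to change.** Amend the outcome definitions under Other outcomes in the Sample Size section:

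1. Define staff time saved as the time of the tests replaced minus the time for CGMS application, removal and any routine site check. Take the CGMS time from a stated estimate or from simple timing fields in RedCap, and leave out study-only tasks. Report time to result as a separate quantity.
2. Report time, blood and ABG-cost savings at 25%, 50%, 75% and 100% of ABGs avoidable, and label the 100% figure an upper bound. This avoids having to adjudicate why each ABG was drawn.
3. List all CGMS cost components, including the receiver and shields, with reusable items charged per use.

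The cost is a few lines of protocol text, a small sensitivity table and, if timing is chosen over an estimate, a few data fields. Those fields should be in place before enrolment, because staff minutes may not be recoverable afterwards. The downside is a less favourable reported saving and a little more analysis.

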#### Data

Because the data are blinded to the nurses and ICU staff, we need to use the web-based Clarity program to be able to download data.

The endocrine department already has an existing Clarity account for clinic patients. Dexcom has given us instructions since they have studies with other institutions. For our study, there will be an account in Clarity. Subject ID can be entered. Clarity can then export data as an Excel file to be imported into RedCap.

The Dexcom G6 gives glucose readings every 5 minutes. The closest glucose reading to the time and date of the blood gas or point of care blood glucose will be matched.

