#### Sanitation

We requested for enough sensors and transmitters for 30 patients.

Should the transmitters fall short for some reason, they can be cleansed with bleach or alcohol

The sensors can only be used for one person each.

The receivers will come with sterile shields which will be changed in-between patients.

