#### **Study Design**

This is a prospective longitudinal study to study the agreement between a novel continuous glucose monitoring system (CGMS) versus current blood glucose monitoring. Subjects in this study will have their blood glucose measured regularly every 1-3 hours with current methods in the CVICU, and by point of care glucose using the Accuchek Inform II on the regular floors, and the CGMS at the same time will be captured. Subjects will have measurements taken throughout their stay in the CVICU and on the regular floors. Agreement and correlation between systems will be calculated, and error will be classified using the Surveillance Error grid. The proportion of errors of at least moderate risk will be calculated.

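### The pairing rule sets no maximum time difference, so a reference glucose in a CGM gap or after early sensor loss is matched to a mistimed reading

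*Combined protocol and SAP*

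**What the plan says.** The combined protocol and SAP gives its only operational pairing rule in the Data section. The sensor reports every 5 minutes, and "The closest glucose reading to the time and date of the blood gas or point of care blood glucose will be matched".

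Two other sections bear on timing. Study Design says that "the CGMS at the same time will be captured" as the standard measurement. Procedure says: "Time-stamped data from the CGMS software will be compared with the correlated ABG or venous of Accu-check Inform II glucose reading". Both show that concurrent pairs are intended; neither gives a tolerance in minutes.

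No section says what to do with a reference that has no concurrent CGM value, or how signal loss, sensor failure or early detachment is handled. Procedure does recognise conditions on which data capture depends: "The receiver has to be within 10-15 feet from the patient", transmission is wireless, and extra adhesive or an overpatch is allowed.

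The pairs feed every accuracy measure in Statistical Methods: the concordance correlation coefficient (CCC), the repeated-measures correlation, and the rate of moderate or worse errors on the Surveillance Error Grid. That last rate sizes the study: "28 subjects (at least 271 paired samples) will be required".

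**The concern.** A nearest-reading rule without a limit always finds a match as long as the subject has one CGM reading. When readings are missing around the reference time, the match is a value from another time. The difference between the two then contains real glucose change as well as measurement error. A single such pair may look better by chance, but on average agreement falls and the error rate rises. The device would be charged with inaccuracy that comes from the matching.

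The rule also hides lost data. A reference with no timely CGM value appears as an ordinary pair, so the report would not show how often the device had nothing to compare, which is useful to know when judging it for hospital use.

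**Working it through.** **1. The plan's own figure.** Inputs from Sample Size: error rate p = 0.05, precision d = 0.05, 95% confidence, m = 10 pairs per subject, ICC = 0.3.

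n = 1.96² × p(1−p)/d² × [1 + (m−1) × ICC] = 72.99 × 3.7 = 270.1, rounded up to 271 pairs; 271/10 = 27.1, rounded up to 28 subjects. This agrees with the plan, and all 32 cells of Table 1 reproduce in the same way. The sample size is not in error.

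**2. Offset produced by the rule.** If the CGM readings on either side of a reference are G minutes apart, the nearest is at most G/2 away, and G/4 on average for a reference at a random time. The share of references more than 5 minutes from any reading is 1 − 10/G for G above 10 minutes, and zero otherwise. Only the 5-minute spacing comes from the documents; the longer ones are illustrations.

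| Spacing G (min) | Largest offset (min) | Mean offset (min) | More than 5 min away |
|---|---|---|---|
| 5 (uninterrupted) | 2.5 | 1.25 | 0% |
| 30 | 15 | 7.5 | 67% |
| 60 | 30 | 15 | 83% |
| 120 | 60 | 30 | 92% |
| 180 | 90 | 45 | 94% |

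After the last reading the offset is the full elapsed time, limited only by how long references continue.

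**3. Effect on the results: illustration only.** The documents give no gap frequency, gap length or glucose variability. Let f be the share of mistimed pairs and q their error rate, both assumed, with 5% errors among correctly timed pairs. The observed rate is 0.05(1−f) + qf.

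- f = 5%, q = 20% to 50%: 5.75% to 7.25%.
- f = 10%, q = 20% to 50%: 6.5% to 9.5%.

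A simulation shows how little can be pinned down. It takes an error-free sensor and assumes mean glucose 140 mg/dL, SD 25 to 35 mg/dL and a time constant of 2 to 4 hours. Inside a 2-hour gap, the share of references more than 20% from their match is 0–3% if glucose changes smoothly and 4–22% under exponential correlation. The 20% cutoff is not an error-grid category. If 5% of references fell in such gaps, a true CCC of 1.00 would read 0.989 to 1.000.

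**4. Precision if untimely references are left unpaired.** With k subjects and m remaining pairs each, the half-width is 1.96 × √{p(1−p)[1 + (m−1) × ICC]/(km)}.

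- 28 subjects, m = 10: √(0.0475 × 3.7/280) × 1.96 = 4.91 points.
- 28 subjects, m = 9 (10% unpaired): √(0.0475 × 3.4/252) × 1.96 = 4.96.
- 28 subjects, m = 8 (20% unpaired): √(0.0475 × 3.1/224) × 1.96 = 5.03.
- 30 subjects, m = 8: √(0.0475 × 3.1/240) × 1.96 = 4.85.

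If losses cluster, the variance term becomes p(1−p) Σmᵢ[1 + (mᵢ−1) × ICC]/(Σmᵢ)².

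- 6 of 28 subjects lose half their pairs: Σ = 814 + 66 = 880 over 250 pairs, half-width 5.07.
- 11 of 28 do: Σ = 629 + 121 = 750 over 225 pairs, half-width 5.20.

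**The case against.** The strongest reply is that the plan's intent is plain. Study Design calls for simultaneous capture, and an analyst who respects that would not pair a reference with a reading hours away. This is right about intent. But the Data section holds the only rule that can be programmed, and followed as written it pairs everything.

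Second, no gap is demonstrated. The documents do not say whether readings taken out of receiver range are lost or recovered later, and Procedure takes steps against dropout (a marked pouch, skin adhesive, an overpatch). This stands: dropout is plausible, but its extent is unknown.

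Third, no decision would change. The plan sets no acceptance threshold. On the simulation's assumed inputs, 5% of references in 2-hour gaps would add at most 0.05 × 22% = 1.1 points to the share more than 20% apart, against a half-width of 4.91 points. This also stands, and it is why the point is minor.

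Two stronger readings are tempting, and the documents do not support them.

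- A reader might infer that the plan itself creates mistimed pairs after day 10, by setting "At the end of 10 days or upon discharge from the hospital, which ever comes first, the sensor/transmitter will be removed" against "Subjects will have measurements taken throughout their stay in the CVICU and on the regular floors". Study Design asks for concurrent capture, which is impossible once the sensor is off. Such references also need a stay at least twice the 4–5 days given as the current average.
- A reader might infer the same fault for references before the first reading. The sensor goes on before anesthesia induction, while the study references are taken in the CVICU and on the floors. The documents describe no start-up delay that would leave those references without readings.

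**Conclusion.** The concern holds as a minor defect in a stated analysis rule. With uninterrupted data there is no problem: the offset is at most 2.5 minutes. With signal loss, or early loss or failure of the sensor, the rule yields pairs up to half the gap apart, or further after the last reading, and these on average understate accuracy in all three measures.

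The size cannot be derived from the documents. The illustrative figures rest wholly on assumed gap shares, error rates and glucose variability. A reader might infer that the accuracy results will be materially biased; the documents give no basis for that. The precision figures, by contrast, use the plan's own assumptions (5% error rate, ICC 0.3, 10 references per subject) together with assumed shares of unpaired references.

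**What to change.** In Data, replace the matching sentence with:

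> A reference value is paired with the closest CGM reading only if that reading is within 5 minutes (one sensor interval) of the recorded reference time. References with no CGM reading in that window are left unpaired, excluded from the accuracy measures, and reported as a number and percentage by setting (CVICU, floor).

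A 5-minute limit loses no pair when data are uninterrupted, and none when a single reading is missed (spacing 10 minutes, largest offset 5). The exact limit is the investigators' choice; what matters is that one is fixed before the data are seen. A second analysis with a 10-minute window is hardly worth adding. If 5% of 280 references (14) fell in 2-hour gaps, only 10/120 = 8% of them, about one pair, would change status.

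The cost is two sentences and one table row. The downside is that some pairs are lost, possibly not at random; the counts by setting help to show this. The half-width stays within the 5-point goal at 10% unpaired and just exceeds it at 20% with 28 subjects, if losses are spread evenly. Clustered losses cost somewhat more. Sanitation says "We requested for enough sensors and transmitters for 30 patients"; enrolling all 30 would bring the 20% case back within the goal, if losses are spread evenly.
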